16.1.4 Safety Studies to be Performed Locally

16.1.4.1 Electrocardiogram

A standard 12-lead ECG should be obtained using equipment provided by the sponsor. The ECG will be obtained after the subject has been in a semi-recumbent position for approximately 10 minutes at the following times:

- Screening
- Just prior (within 30 minutes) to the start of the first infusion of the first dose of test article ($t = 0$ h on [Table 1](#))
- 30-90 minutes after the start of the first infusion of the first dose of test article

- Just prior (within 30 minutes) to the start of the first infusion of the third dose of test article ($t = 24$ h on [Table 1](#))
- 30-90 minutes after the start of the first infusion of the third dose of test article
- At the Day 7 visit
- At the EOT visit
- In any case in which a subject develops an AE of non-pleuritic cardiac chest pain, palpitations, tachyarrhythmia or as otherwise clinically indicated (see [Section 16.1.2](#))

Reading and interpretation of the ECG will be performed centrally and provided to the investigator. The investigator is responsible for reviewing interpretations and for retaining hard copies of the reports.

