22.7.3 Electrocardiograms

Electrocardiogram data (RR interval, PR interval, QRS interval, Corrected QT interval [QTc], QTc Bazzett's Correction Formula [QTcB], and QTc Fridericia's Correction Formula [QTcF]) will be summarized descriptively at each scheduled evaluation and for the overall worst post-Screening value. Changes from Screening at each visit will also be provided. An outlier analysis will be conducted based on the worst post-Screening value.

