8 OVERALL STATISTICAL CONSIDERATIONS

8.1 General Conventions

The following general comments apply to all statistical analyses and data presentations:

- Summaries will include frequency and percentages for categorical data; frequency and median for ordinal data; and frequency, mean, standard deviation, and median, minimum, and maximum for quantitative data.
- Duration variables will be calculated using the general formula (end date – start date) +1.
- Change from baseline will be calculated for each subject at the specified time point as the value at the specified time point minus the baseline value.
- If the reported value of a clinical laboratory parameter cannot be used in a statistical summary table (eg, a character string is reported for a parameter of the numerical type), a coded value must be appropriately determined and used in the statistical analyses. In general, a value or lower and upper limit of normal range such as ‘< 10’ or ‘≤ 5’ will be treated as ‘10’ or ‘5’ respectively, and a value such as ‘> 100’ will be treated as ‘100.’ However, the actual values as reported in the database will be presented in data listings. Data will be reviewed on an ongoing basis in a blinded manner to assess the frequency of occurrence of laboratory parameters reported as a character string.
- Individual subject listings of all data represented on the eCRFs will be provided to facilitate the investigation of tabulated values and to allow for the clinical review of all efficacy and safety parameters.
- Version 9.3 (or higher) of SAS® statistical software package will be used to provide all summaries, listings, graphs, and statistical analyses.

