11.2 Vital Signs

Blood pressure (systolic and diastolic), respiratory rate, temperature, and pulse/heart rate will be summarized using descriptive statistics at the following time points: prior to each infusion while the subject is on iv treatment, EOT Visit, PTE Visit, and highest and lowest post-baseline value. Heart rate and blood pressure will be summarized for the following additional time points: for the first 3 doses of test article, just prior to the first infusion, within 30 to 90 minutes after the start of the first infusion and 3.5 to 5.5 hours after the start of the first infusion. Descriptive statistics of the change from baseline to each post-baseline time point and the highest and lowest post-baseline value will also be provided. Baseline is defined as the value closest to but prior to the initiation of test article administration. If no value is available prior to the initiation of test article administration, a value within 2 hours after initiation of test article administration.

Post-baseline vital signs will be defined as clinically notable (CN) if they meet the criterion value or both the criterion value and the change from baseline criterion listed in [Table 8](#). The incidence of CN vital signs will be summarized by time point and treatment group, and will be listed and flagged in by-subject listings. The overall post-baseline incidence of CN values for each vital sign parameter, which includes values from unscheduled post-baseline visits, will also be summarized. A listing will also be provided of subjects with a CN vital sign and will list all values for a vital sign noted as CN.

Table 8. Criteria for Treatment Emergent Clinically Notable Vital Signs

Vital Sign Parameter	Flag	Criterion Value	Change from Baseline
Systolic Blood Pressure (mmHg)	High (CH)	≥ 180	Increase of ≥ 20 mmHg
	Low (CL)	≤ 90	Decrease of ≥ 20 mmHg
Diastolic Blood Pressure (mmHg)	High (CH)	≥ 105	Increase of ≥ 15 mmHg
	Low (CL)	≤ 50	Decrease of ≥ 15 mmHg
Heart Rate (bpm)	High (CH)	≥ 120	Increase of ≥ 15 bpm
	Low (CL)	≤ 50	Decrease of ≥ 15 bpm
Temperature (°C)	Low (CL)	<36.0	NA
	High (CH)	>38.0	NA

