11.3 Electrocardiogram

A central vendor with readers blinded to treatment assignment will perform the reading of the ECGs. The central ECG results will be used for the statistical analyses.

Descriptive statistics for ECG parameters (heart rate, RR interval, PR interval, QRS interval, QT interval, and QTc interval) at baseline, 30 to 90 minutes after the start of the first infusion of the first and third doses of test article, Day 7 (+1 day), and at the EOT Visit, and the change from baseline will be presented by treatment group. The QTc interval will be presented by both the Bazett ($QTcB = QT/(RR)^{1/2}$) and the Fridericia ($QTcF = QT/(RR)^{1/3}$) corrections. The change from baseline to the minimum and maximum post-baseline values will also be summarized by treatment group. Baseline is defined as the value closest to but prior to the initiation of test article administration. If no value is available prior to the initiation of test article administration, a value within 2 hours after initiation of test article administration.

The number and percentage of subjects with any post-baseline increase in QTcF and any post-baseline increase of > 30 msec or > 60 msec in QTcF will be summarized by treatment group. The number and percentage of subjects with a baseline QTcF ≤ 450 msec and with a post-baseline QTcF of > 450 msec and with a baseline QTcF ≤ 500 and with a post-baseline QTcF of > 500 msec will also be summarized by treatment group. The number and percentage of subjects with a post-baseline increase in QTcF of > 30 msec resulting in a post-baseline QTcF of > 450 msec or > 500 msec will also be summarized by treatment group. A listing will also be provided of subjects with a QTcF that meets one of the criteria listed above and will list all QTcF values for the subject.

The distribution of QTcF values (≤ 450 msec, $> 450 - \leq 480$ msec, $> 480 - \leq 500$ msec, and > 500 msec) at each time point and the distribution of change from baseline in QTcF values at each time point (0 or less [no increase], 1-29 msec, 30-60 msec, and > 60 msec) will be summarized by treatment group.

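### Heart-rate, blood-pressure and ECG changes after later doses are taken only from the pre-first-dose value, and the SAP's time-point summaries omit the scheduled pre-dose-3 ECG

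*Combined protocol and SAP*

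**What the plan says.** SAP 8.1 sets the general rule: "Change from baseline will be calculated for each subject at the specified time point as the value at the specified time point minus the baseline". SAP 11.2 applies it to vital signs: "Descriptive statistics of the change from baseline to each post-baseline time point and the highest and lowest post-baseline value will also be provided". There is one reference for every time point: "Baseline is defined as the value closest to but prior to the initiation of test article administration". If no such reading exists, one taken up to 2 hours after dosing starts may be used. SAP 11.3 uses the same reference for ECG.

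The data collected around the early doses would support more than this:

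- **Heart rate and blood pressure.** Protocol v2.0, 16.1.2, takes readings before, 30-90 minutes after and 3.5-5.5 hours after the start of each of doses 1, 2 and 3. SAP 11.2 summarizes these time points ("for the first 3 doses of test article, just prior to the first infusion, within 30 to 90 minutes", then the later reading), but as values and as changes from the single baseline.
- **ECG.** Protocol v2.0, 16.1.4.1, schedules recordings before and after doses 1 and 3, including one "Just prior (within 30 minutes) to the start of the first infusion of the third dose of test article". SAP Appendix 1 (footnote o) repeats this. The time points listed in SAP 11.3 are baseline, "30 to 90 minutes after the start of the first infusion of the first and third doses of test article", Day 7 and EOT.
- **Protocol commitment.** Protocol v2.0, 22.7.3, says ECG data "will be summarized descriptively at each scheduled evaluation and for the overall worst post-Screening value". SAP Section 7 declares one departure from the protocol, the expanded microITT population, and nothing about ECG.

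**The concern.** The documented acute signal for omadacycline is a transient rise in heart rate in the hours after dosing. Protocol 9.1 reports mean rises of up to 15-20 bpm over placebo in Phase 1. In Phase 2, after the first infusion, it reports +2.5 bpm against -0.1 bpm for linezolid (p = 0.005). Readings before and after each early dose are what is needed to measure such an effect.

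Subjects enter acutely ill, and a heart rate above 90 bpm is one of the four qualifying vital signs. If heart rate settles over the first day, a change from the first baseline after dose 2 or 3 combines recovery with the effect of that dose. An arm could then show a mean fall after dose 3 even if the dose raises heart rate, and fewer individuals would cross a threshold for a rise. The clinically notable rule in SAP Table 8 uses the same reference. For ECG, the omitted time point means that even a mean before-to-after comparison at dose 3 cannot be read from the planned tables.

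**Working it through.** **1. ECG time points, side by side**

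| Recording | Protocol 16.1.4.1 | SAP 11.3 list |
|---|---|---|
| Before dose 1 (baseline) | yes | yes |
| 30-90 min after dose 1 | yes | yes |
| Before dose 3 | yes | no |
| 30-90 min after dose 3 | yes | yes |
| Day 7, EOT | yes | yes |

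No ECG is scheduled around dose 2. This part needs no assumption.

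**2. Algebra for heart rate after dose 3**

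Let b be baseline, r the fall in heart rate before dose 3, and a the acute rise from the dose.

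- Pre-dose 3 = b - r, and post-dose 3 = b - r + a.
- Change from baseline = a - r. Change from the same dose's pre-dose value = a.
- Arm difference in change from baseline, with no acute effect in the comparator = (a - r) - (0 - r) = a if r is equal in both arms.

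**3. Inputs for the size**

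- From protocol 9.1: a = 2.5 + 0.1 = 2.6 bpm (Phase 2), and a = 15 bpm (lower end of the Phase 1 maximum).
- Within-dose SD, back-solved from the Phase 2 p-value assuming a two-sided z test with 111 and 108 subjects: SE = 2.6/2.807 = 0.926; SD = 0.926/sqrt(1/111 + 1/108) = 6.9 bpm.
- Assumed, not in the documents: r = 0 to 20 bpm, baseline mean 100 and SD 15 bpm, day-to-day SD 8 bpm.

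**4. Results** (means by algebra; percentages from 400,000 simulated subjects per scenario)

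| Recovery r (bpm) | 0 | 5 | 10 | 15 | 20 |
|---|---|---|---|---|---|
| Mean change from baseline, a = 2.6 | 2.6 | -2.4 | -7.4 | -12.4 | -17.4 |
| Mean change from baseline, a = 15 | 15 | 10 | 5 | 0 | -5 |
| Comparator, mean change from baseline | 0 | -5 | -10 | -15 | -20 |
| Rise >= 15 from baseline, a = 15 | 50% | 32% | 17% | 8% | 3% |
| Rise >= 15 from pre-dose, a = 15 | 50% | 50% | 50% | 50% | 50% |
| >= 120 and rise >= 15 from baseline, a = 15 | 29.1% | 17.2% | 8.9% | 3.8% | 1.4% |
| >= 120 and rise >= 15 from pre-dose, a = 15 | 25.6% | 19.8% | 14.7% | 10.2% | 6.6% |
| Rise >= 15 from baseline, a = 2.6 | 12.0% | 4.9% | 1.6% | 0.4% | 0.1% |
| Rise >= 15 from pre-dose, a = 2.6 | 3.5% | 3.5% | 3.5% | 3.5% | 3.5% |

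Check of one cell (a = 15, r = 10): the SD of change from baseline is sqrt(8^2 + 6.85^2) = 10.5, and P(Z >= (15 - 5)/10.5) = 17%.

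In every row the arm difference in mean change stays at a. With little recovery, the baseline-referenced count can exceed the same-dose count, because day-to-day variation is added to it. The counts are diluted as r grows.

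**5. One subject under Table 8**

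Take 110 bpm at baseline, 88 before dose 3 and 122 after it. The rise from baseline is 122 - 110 = 12; the rise from pre-dose is 122 - 88 = 34. SAP 11.2 lets a value be notable on the criterion value or on both value and change, without saying which applies when. If both are required (>= 120 bpm and a rise >= 15 bpm), this subject is not flagged. If the value alone suffices, 122 is flagged.

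**6. Precision (illustrative)**

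With equal SDs, the variance of a change is 2 x SD^2 x (1 - correlation). The variance ratio, same-dose to baseline change, is therefore (1 - r_pre)/(1 - r_base), and the SD cancels. For assumed correlations of 0.7-0.8 with pre-dose and 0.4-0.5 with baseline, it runs from 0.2/0.6 = 0.33 to 0.3/0.5 = 0.60. As an example, with SD 15 bpm, 750/2 = 375 per arm and correlations 0.5 and 0.75, the change SDs are 15.0 and 10.6 bpm. The standard errors of the arm difference, SD x sqrt(2/375), are 1.10 and 0.77 bpm.

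**The case against.** The strongest reply is that the trial is randomized. Recovery common to both arms cancels in the comparison, so the mean arm difference after doses 2 and 3 still estimates the acute effect. SAP 11.2 also summarizes the pre-dose heart rates for doses 2 and 3, so a reader can subtract arm means. At dose 1 the baseline is normally the reading just before the infusion, so that change is already within-dose, and it corresponds to the Phase 2 result. A single reference is conventional, and protocol 22.7.2 and 22.7.3 themselves plan change from Screening. These are descriptive summaries with no planned test.

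Most of this stands, and it limits the point. It does not remove it. SAP 11.2 plans no arm difference or interval, and subtracting means gives neither the SD of the within-dose change nor a count of subjects. Equal recovery is itself an assumption. For ECG, the pre-dose-3 mean is not among the listed summaries, so subtraction is not available.

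A reader might infer four stronger things that the documents do not support:

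- **That the baseline is febrile.** Entry needs two of four abnormal vital signs, and neither fever nor a raised heart rate is mandatory.
- **That QTcF rises are hidden, including after dose 2.** No ECG is scheduled around dose 2, and the documents give no direction for QTcF drift during recovery, so a rise at dose 3 could be understated or overstated.
- **That the pre-dose-3 ECG is discarded.** It is post-baseline, so it can enter the minimum and maximum summaries and the any-post-baseline QTcF counts. SAP 11.3 also promises QTcF distributions at each time point, but the only list of time points leaves this one out.
- **That the 122 bpm subject is certainly missed.** Table 8 gives a change threshold for every parameter except temperature, which makes the two-part reading more natural, but the text does not settle it.

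**Conclusion.** The point holds in a limited form. Established from the text alone: every planned change uses one pre-first-dose value; no same-dose change is planned for heart rate and blood pressure at doses 2-3 or for ECG heart rate and QTcF at dose 3; and SAP 11.3 omits a scheduled ECG from its time points, contrary to protocol 22.7.3 and undeclared in SAP Section 7.

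Dilution of within-arm means follows by algebra once there is any recovery: with a = 2.6 bpm, the mean change turns negative when recovery exceeds 2.6 bpm. How far it goes, and the effect on counts (17% against 50% for a rise of at least 15 bpm at a = 15 and r = 10), rests on assumed recovery and SDs. A fall in heart rate by the later doses is plausible, but the documents give no size. It would be wrong to conclude that the trial cannot detect an acute heart-rate effect, because the dose-1 change and, under equal recovery, the arm difference both remain informative. The efficacy analyses and the sample size are not affected.

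**What to change.** 1. In SAP 11.3, add the pre-dose-3 ECG as a summarized time point, which brings the section into line with protocol 22.7.3. Add the change in heart rate and QTcF from pre-dose 3 to 30-90 minutes after dose 3.
2. In SAP 11.2, for doses 2 and 3, add the change in heart rate and blood pressure from the same dose's pre-dose reading to the 30-90 minute and 3.5-5.5 hour readings, by arm, with the arm difference and 95% CI.
3. Add a supplementary clinically notable heart-rate row that applies the existing Table 8 thresholds with the same-dose pre-dose value as reference. State for each Table 8 parameter whether the value alone or both value and change are required.

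Keep the existing change-from-baseline tables and list the added analyses in SAP Section 7. The cost is SAP wording and a few descriptive tables from data already collected, with no new assessments, visits or subjects.

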12.1 Inclusion Criteria

To be eligible for randomization in this study, a subject must fulfill ALL of the following criteria:

1. Written and signed informed consent must be obtained before any protocol specific assessment is performed.
2. Male or female, aged 18 years or older
3. Has at least 3 of the following symptoms:
 - Cough
 - Production of purulent sputum
 - Dyspnea (shortness of breath)
 - Pleuritic chest pain.
4. Has at least TWO of the following abnormal vital signs
 - Fever or hypothermia documented by the investigator (temperature $> 38.0^{\circ}\text{C}$ [100.4°F] or $< 36.0^{\circ}\text{C}$ [95.5°F])
 - Hypotension with systolic blood pressure (SBP) < 90 mm Hg
 - Heart rate > 90 bpm
 - Respiratory rate (RR) > 20 breaths/minute.
5. Has at least 1 clinical sign or laboratory finding associated with CABP:
 - Hypoxemia (partial pressure of arterial oxygen [PaO_2] < 60 mm Hg by arterial blood gas [ABG] or oxygen saturation $< 90\%$ by pulse oximetry)
 - Physical examination findings of pulmonary consolidation (eg, dullness on percussion, bronchial breath sounds, or egophony)
 - An elevated total white blood cell (WBC) count ($> 12,000$ cells/ mm^3) *or* leucopenia ($\text{WBC} < 4,000$ cells/ mm^3) *or* elevated immature neutrophils ($> 15\%$ band forms, see % bands calculation in [Appendix 4](#), regardless of total peripheral WBC count).
6. Radiographically-confirmed pneumonia, ie, new or progressive pulmonary infiltrate(s) on chest X-ray (CXR) or chest computed tomography (CT) scan consistent with acute bacterial pneumonia within 24 hours prior to the first dose of test article.
7. Has disease categorized as being PORT Risk Class II, III, or IV at Screening (see PORT Risk Class calculation in [Appendix 2](#)).
8. Is expected to require a minimum of at least 3 days of iv therapy for the initial treatment of CABP.
9. Females must have a negative urine pregnancy test at Screening and agree to comply with using an acceptable method of birth control as per your local requirements (eg, abstinence, po contraceptive, intrauterine device [IUD], barrier contraception [condom], tubal ligation, hysterectomy, bilateral oophorectomy, postmenopausal or vasectomized partner) from Screening through post therapy evaluation (PTE). Males must agree to use an acceptable method of birth control with female partner(s) and must not donate sperm from Screening through PTE.

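### The SAP's clinically notable vital-sign rule is ambiguous: read literally, the change-from-baseline column does nothing, and under either reading some persisting entry abnormalities count as treatment-emergent

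*Combined protocol and SAP*

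**What the plan says.** SAP 11.2 applies the flag to post-baseline values, which are clinically notable "if they meet the criterion value or both the criterion value and the change from baseline criterion" listed in Table 8. That table is titled "Criteria for Treatment Emergent Clinically Notable Vital Signs". It gives a criterion value and a change for systolic pressure, diastolic pressure and heart rate, high and low. High heart rate is ≥ 120 bpm with "Increase of ≥ 15 bpm"; low systolic pressure is ≤ 90 mmHg with "Decrease of ≥ 20 mmHg". Temperature has limits of < 36.0 and > 38.0 °C, with NA as the change in both rows.

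The section does not say which half of the *or* governs which parameter, or whether two versions are to be tabulated. Protocol v2.0 section 22.7.2 leaves the criteria to the SAP, so it does not settle the matter.

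Inclusion Criterion 4 (protocol v2.0, section 12.1) reads "Has at least TWO of the following abnormal vital signs". Its list includes "Hypotension with systolic blood pressure (SBP) < 90 mm Hg", "Heart rate > 90 bpm" and a temperature above 38.0 or below 36.0 °C.

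**The concern.** A table of treatment-emergent events should separate what appeared or worsened on treatment from what the subject brought into the trial. That matters here because entry requires at least two abnormal vital signs. PORT scoring (protocol v2.0, Appendix 2) also awards points for pulse ≥ 125, SBP < 90 and temperature ≥ 40 or < 35 °C, so entry values beyond the Table 8 limits are foreseen. Heart rate and blood pressure are measured 30–90 minutes and 3.5–5.5 hours after the start of the first infusion for each of the first three doses, when some entry abnormalities may still be present.

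Two programmers could follow the same sentence and produce different tables. Background carried over from baseline would fall on both arms and bring their flagged proportions closer together. Heart rate is where a reader would look first: protocol section 9.1 reports Phase 1 mean rises of up to 15–20 bpm and a smaller Phase 2 effect (+2.5 v −0.1 bpm).

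The SAP builds baseline in elsewhere. Treatment-emergent adverse events must be new, more frequent or worse (11.1). The QTcF threshold-crossing counts condition on baseline or require a minimum increase (11.3). Laboratory results are summarized by a rise of at least 2 grades, and transaminase elevations among subjects normal at baseline (11.4).

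**Working it through.** The plan gives no figure to reproduce. The check concerns logic, then the Table 8 limits applied to example values.

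**1. Logic.** Let A be the criterion value met and B the change criterion met.

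| A | B | A or (A and B) | A and B |
|---|---|---|---|
| no | no | no | no |
| no | yes | no | no |
| yes | no | **yes** | **no** |
| yes | yes | yes | yes |

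The third column equals A in every row. As a further check, the literal high-heart-rate rule was compared with the value ≥ 120 alone for every whole-number baseline from 60 to 160 and post-baseline value from 60 to 180 (101 × 121 = 12,221 pairs). They differed in 0 pairs.

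**2. Two readings applied to examples.** *Literal* is A or (A and B). *Row by row* is A alone where change is NA, and A and B where a change is listed.

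| Parameter | Baseline | Post-baseline | Change | Literal | Row by row |
|---|---|---|---|---|---|
| Heart rate, high | 110 | 110 | 0 | no | no |
| Heart rate, high | 119 | 119 | 0 | no | no |
| Heart rate, high | 122 | 122 | 0 | **flag** | no |
| Heart rate, high | 130 | 121 | −9 | **flag** | no |
| Heart rate, high | 106 | 120 | +14 | **flag** | no |
| Heart rate, high | 105 | 120 | +15 | flag | flag |
| SBP, low | 88 | 88 | 0 | **flag** | no |
| SBP, low | 85 | 90 | +5 | **flag** | no |
| SBP, low | 110 | 90 | −20 | flag | flag |
| Temperature, high | 39.0 | 38.5 | −0.5 | flag | **flag** |
| Temperature, low | 35.8 | 35.8 | 0 | flag | **flag** |

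Under the literal reading, a heart rate falling from 130 to 121 and a systolic pressure rising from 85 to 90 are both counted as treatment-emergent. Under the row-by-row reading these disappear, but a fever that is falling is still counted.

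**3. Size.** The documents give neither the share of subjects beyond the limits at baseline nor the share in whom this persists, so no count can be derived. As an illustration only, for the literal reading: assume new high heart rate in 6% v 2% of subjects, and let b be the proportion in each arm at ≥ 120 both before and after dosing. The flagged proportion is b + (1 − b)p.

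| b | 6% arm | 2% arm | Ratio |
|---|---|---|---|
| 0 | 6.0% | 2.0% | 3.0 |
| 0.05 | 0.05 + 0.95 × 0.06 = 10.7% | 0.05 + 0.95 × 0.02 = 6.9% | 1.55 |
| 0.10 | 0.10 + 0.90 × 0.06 = 15.4% | 0.10 + 0.90 × 0.02 = 11.8% | 1.31 |
| 0.20 | 0.20 + 0.80 × 0.06 = 24.8% | 0.20 + 0.80 × 0.02 = 21.6% | 1.15 |

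All inputs are assumptions; neither 6% v 2% nor any value of b comes from the documents. Vital signs are analyzed descriptively, so a power calculation would describe a test the plan does not perform.

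**The case against.** The strongest reply is that the sentence has a sensible meaning. Table 8 has two kinds of row, and the *or* can simply distinguish them: value alone for temperature, both conditions for the rest. That reading is natural, and under it the change column acts for blood pressure and heart rate. A reader might infer that the column can never act; that holds only for the literal reading. What stands against the reply is that the SAP nowhere says which meaning applies.

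Three further inferences go beyond the documents:

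- *All entry tachycardia is counted.* It is not. Entry needs a rate above 90, but the flag needs ≥ 120 after baseline, so unchanged rates of 91–119 are never flagged. Any entry abnormality must persist or recur to count. Exclusion 7 removes subjects presenting with tachyarrhythmia, and Exclusion 11 those needing acute pharmacologic blood-pressure support.
- *The fever problem comes from the same wording.* It comes from the NA entries and would remain if only the sentence were repaired.
- *A real heart-rate effect would be hidden.* The plan also summarizes change from baseline in heart rate at the timed post-infusion readings and at the highest and lowest values, ECG heart rate and its change (11.3), and adverse events (11.1). The Phase 2 effect was itself reported as a mean change. The listing prints all values of a flagged vital sign, so an abnormal baseline would be visible.

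**Conclusion.** The point holds as a defect in a stated rule with limited reach. Read literally, the definition reduces to the criterion value alone and makes six printed change criteria inert. Read row by row, it works for blood pressure and heart rate but still labels persisting entry fever or hypothermia treatment-emergent. No reading apparent in the text agrees fully with the table's title.

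The choice changes which subjects are counted in the clinically notable incidence table, by time point and overall, and in its listings. It touches no efficacy result, decision rule or formal test. The number of subjects involved is unknown, and the illustrative ratios show the direction of dilution under one reading, not its size in this trial. The logic itself rests on no assumption. It should be corrected because the rule cannot be programmed unambiguously as written and the correction is nearly free.

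**What to change.** Replace the sentence in SAP 11.2 with a rule by parameter:

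- Systolic pressure, diastolic pressure and heart rate are clinically notable only when a post-baseline value meets both the criterion value and the change criterion in Table 8.
- Temperature is clinically notable only when a post-baseline value meets the limit and the baseline value did not. Alternatively, keep the value-only rule for temperature and remove the treatment-emergent label from those rows.

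If the sponsor also wants value-only counts for blood pressure and heart rate, tabulate them separately under a title that does not say treatment-emergent.

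The cost is one sentence in 11.2, a matching adjustment to Table 8 if the label is dropped for temperature, and one programmed flag. No new data are needed. The change should be made before unblinding.
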